15.2.3. Short Form Health Survey (SF-12)

SHORT FORM HEALTH SURVEY (SF-12)

Sponsor: Fundación Investigación HM Hospitales

Principal Investigator: [name] [name]

Protocol Code: EPIPUL

Form Version: 1.0 of 26th of July 2019

This survey asks for your views about your health. This information will help keep track of how you feel and how well you are able to do your usual activities. Please answer every question by marking one box. If you are unsure about how to answer, please give the best answer you can.

1. In general would you say your health is:

Excellent

Very Good

Good

Fair

The Poor

The following questions are about activities you might do during a typical day. Does your health now limit you in these activities? If so, how much?

2. Moderate activities, such as moving a table, pushing a vacuum cleaner, cowling, or playing golf:

Yes, limited a lot

Yes, limited a little

No, not limited at all

3. Climbing several flights of stairs:

Yes, limited a lot

Yes, limited a little

No, not limited at all

During the past week, have you had any of the following problems with your work or other regular daily activities as a result of physical health?

4. Accomplished less than you would like:

Yes

No

5. Were limited in the kind of work or other activities

Yes

No

During the past week, have you had any of the following problems with your work or other regular daily activities as a result of any emotional problems (such as feeling depressed or anxious)?

6. Accomplished less than you like:

Yes

No

7. Didn't do work or other activities as carefully as usual:

Yes

No

8. During the past week, how much did pain interfere with your normal work (including both work outside the home and housework)?

Not at all

A little bit

Moderately

Quite a bit

Extremely

These questions are about how you feel and how things have been with you during the past week. For each question, please give the one answer that comes closest to the way you have been feeling. How much of the time during the past week

9. Have you felt calm and peaceful?

All of the time

Most of the time

A good bit of the time

Some of the time

A little of the time

None of the time

10. Did you have a lot of energy?

All of the time

Most of the time

A good bit of the time

Some of the time

A little of the time

None of the time

11. Have you felt downhearted and blue?

All of the time

Most of the time

A good bit of the time

Some of the time

A little of the time

None of the time

12. During the past week, how much of the time has your physical health or emotional problems interfered with your social activities (like visiting with friends, relatives, etc.)?

All of the time

Most of the time

A good bit of the time

Some of the time

A little of the time

None of the time

15.2.4. Short Form Health Survey (SF-12)

Patient General Impression of Improvement (PGI-I)

Sponsor: Fundación Investigación HM Hospitales

Principal Investigator: [name] [name]

Protocol Code: EPIPUL

Form Version: 1.0 of 26th of July 2019

Since the beginning of the study, my general state of health

Very much improved

Much improved

Minimally improved

No change

Minimally worse

Very much worse

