10. Primary Endpoint:	Difference in pain reduction between the control group and the experimental group since the baseline visit and the 6 month visit evaluated by Visual Analogue Scale (VAS).
11. Secondary Endpoints:	
Change from Baseline in pain at 1, 2 and 4 months (Visual Analogue Scale, VAS).Change from Baseline in disability at 1, 2 and 6 months (assessed by Oswestry Disability Index, ODI).Change from Baseline in health survey at 1, 2, 4 and 6 (assessed by Short Form Health Survey, SF-12).Change from Baseline in neuropathic pain at 1, 2 and 6 months (assessed by Douleur Neuropathique 4 Questions, DN4).Change from Baseline in improvement of pain at 1, 2, 4 and 6 months (assessed by Patient Impression of Improvement, PGI-I).Assessment of subject satisfaction with experimental procedure 2 and 6 months.Incidence of unanticipated adverse device effects.Change in opioid intake in 6 months.Adverse events related to procedures (experimental group and control group).
12. Study Design:	Prospective, randomized, single-blind and multi-centre study. Controlled comparison between epidural steroids injection with catheter and epidural radiofrequency by catheter in the epidural space plus steroids administration. After the treatment, patients will be followed-up at 1, 2, 4 and 6 months.

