5.3 Secondary Endpoints

- 5.3.1. Change from Baseline in pain at 1, 2 and 4 months (assessed by Visual Analogue Scale, VAS).
- 5.3.2. Change from Baseline in disability at 1, 2 and 6 months (assessed by Oswestry Disability Index, ODI).
- 5.3.3. Change from Baseline in health survey at 1, 2, 4 and 6 months (assessed by Short Form Health Survey, SF-12).
- 5.3.4. Change from Baseline in neuropathic pain at 1, 2 and 6 months (assessed by Douleur Neuropathique 4 Questions, DN4).
- 5.3.5. Assessment of improvement of pain with experimental procedure at 1, 2, 4 and 6 months (assessed by Patient Impression of Improvement, PGI-I).
- 5.3.6. Incidence of unanticipated adverse device effects.
- 5.3.7. Change in opioid intake in 6 months.
- 5.3.8. Adverse events related to procedures (experimental group and control group).
- 5.3.9. Assessment of subject satisfaction with experimental procedure at 2 and 6 months.

6. - ELIGIBILITY CRITERIA

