7.6 Evaluation Endpoints

▪ Primary endpoint

Visual Analogue Scale (VAS): The VAS measures the pain intensity reported by the subject. Subject scores the intensity of pain on a 10 mm line. The VAS in this study consists of a 10 mm line with one indicating “No Pain” and the other end indicating “Worst imaginable pain”. Upon completion by the subject VAS scores will be measured and converted to a numeric value (0.0 mm to 10.0 mm) by site staff personnel. VAS is the most widely used outcome measure in assessing pain due to its documented reliability and validity, ease in administration, and minimal training requirements for the administrator.

Subjects will complete a mean VAS score for leg and back pain: at Baseline, months 1, 2, 4, 6 and if applicable at the Unscheduled visit. The change in leg and back pain VAS scores, the percentage change in leg and back pain VAS scores, and the responder rate for leg and back pain will be calculated and summarized for each visit.

▪ Secondary Endpoints.

- Oswestry Disability Index (ODI): The ODI measures functional disability as reported by the subject. Subjects will complete ODI during the study visits: at Baseline, months 1, 2, 6 and if applicable at the Unscheduled visit. The changes in functional disability will be summarized as continuous variables.

- Short Form Health Survey (SF-12): The SF-12 measure health status reported by subject at: Baseline, months 1, 2, 4, 6 and if applicable at the Unscheduled visit. The changes in health status will be summarized as continuous variables.

- Douleur Neuropathique 4 Questions (DN4): The DN4 measures the neuropathic pain reported by the subject. Subjects will complete DN4 during the study visits: at Baseline, months 1, 2, 6 and if applicable at the Unscheduled visit. The changes in neuropathic pain will be summarized as continuous variables.

- Patient Impression of Improvement questionnaire (PGI-I): The PGI-I measure subjective improvement in pain. Subjects will complete PGI-I form during the study visits at: month 1, 2, 4, 6 and if applicable at the Unscheduled visit.

- Medication Usage: morphine equivalent units of opioid medications; other non-opioid pain medications. Assessed at: Baseline, months 1, 2, 4, 6 and if applicable at the Unscheduled visit.

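### The PGI-I form asks about general health, but sections 1, 5.3.5 and 7.6 define its endpoint as improvement in pain

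*Combined protocol and SAP*

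**What the plan says.** Three places in the protocol describe the PGI-I as a measure of pain:

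- Section 1, item 11 (summary of secondary endpoints): "Change from Baseline in improvement of pain at 1, 2, 4 and 6 months", assessed by PGI-I.
- Section 5.3.5: "Assessment of improvement of pain with experimental procedure at 1, 2, 4 and 6 months", again assessed by PGI-I.
- Section 7.6: "The PGI-I measure subjective improvement in pain".

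The timing is consistent throughout. Section 7.6 states: "Subjects will complete PGI-I form during the study visits at: month 1, 2, 4, 6 and if applicable at the Unscheduled visit". The visit plan in 7.5 and Table 1 agree.

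The form is in Annex II at 15.2.4, version 1.0 of 26 July 2019. It sits under a section heading that names the SF-12, although the title below that heading is the PGI-I. The stem is "Since the beginning of the study, my general state of health". As read, six responses follow: three grades of improvement, no change, and two grades of worsening.

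Section 13 gives no scoring, test or summary for the PGI-I, and no section says how many response categories it should have.

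**The concern.** The endpoint and its instrument name different things. The endpoint is the patient's own judgement of whether pain has improved. The form asks whether general health has changed. In this population health can move without pain, through other illness, medication effects or mood, and pain can move without much change in overall health. If the plan is followed as written, the report would present answers about health as evidence on pain.

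The stem also starts the clock in a different place. Section 5.3.5 concerns improvement with the procedure, whereas the form counts from the start of the study. A patient could take that to mean screening, which comes before treatment.

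Answers given to the wrong question cannot be converted afterwards, so the mismatch is cheap to correct before the form is used and not correctable for answers already given.

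**Working it through.** **1. Definition against form**

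| Feature | Sections 1, 5.3.5, 7.6 | Form at 15.2.4 |
|---|---|---|
| What is rated | Improvement in pain | General state of health |
| Mention of pain | Yes, in all three | None |
| Reference point | With the procedure (5.3.5) | Beginning of the study |
| Visits | Months 1, 2, 4, 6 | Same, by 7.5, 7.6 and Table 1 |

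The visits match. What is rated does not, and neither does the reference point.

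**2. Reference point.** Section 7.5.2 allows baseline up to 30 days after screening. Section 7.5.3 makes treatment a separate visit with a window of 15 days either way, although baseline and treatment may coincide. The start of the study and the treatment can therefore fall weeks apart.

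**3. Does another form ask the same question?**

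- The VAS form asks for average pain over the last 7 days.
- ODI section 1 asks about pain at the moment.
- SF-12 question 8 asks how far pain interfered with work in the past week.

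Each records a state at one time. None asks the patient to judge whether pain has changed. The protocol also lists VAS change (5.3.1) and PGI-I improvement (5.3.5) as separate endpoints.

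**4. Number of answers affected.** Inputs are 124 patients and 20% losses (section 7.3), and four scheduled visits (section 7.6).

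- No losses: 4 × 124 = 496.
- 20% lost at every visit: 124 × 0.80 = 99.2, about 99 per visit; 4 × 99 = 396.

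The range is about 396 to 496, not counting unscheduled visits. It counts answers to the wrong question and does not measure bias.

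**5. Sample size.** The plan's figure reproduces and does not involve the PGI-I. With means of 40 and 60 mm and SD 30 mm, the standardised difference is 20/30. A two-sided t-test at 5% with 90% power needs 48.26, so 49 per group. Allowing for losses, 49/(1 − 0.20) = 61.25, so 62 per group and 124 in total, as section 7.3 states.

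**6. Response list.** As read there are 3 improved + 1 unchanged + 2 worse = 6 options. The option "much improved" has no counterpart on the other side: the list goes from "Minimally worse" straight to its most extreme option.

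**The case against.** A reader might infer that the pain-improvement endpoint goes unmeasured at every visit. The documents do not support that. The endpoint is defined as assessed by the PGI-I, and the form is scheduled at all four follow-up visits. Data will exist, but on a broader concept than the one defined.

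The consequence is also limited. VAS is scheduled at months 1, 2, 4 and 6, so pain scores do not depend on this form. No test or decision rule is attached to the PGI-I, so no confirmatory conclusion changes. This stands, and it confines the point to one secondary endpoint. It does not remove the point, because no printed form asks for the patient's judgement of change in pain.

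The form may be right and the endpoint wording wrong, since the form's own title refers to a general impression. This is a fair alternative, and the fix allows for it.

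A reader might also blame the short response list for the mismatch. It is not the cause: an uneven list makes worsening coarser but does not change what is rated. The text was machine-read, so a dropped line cannot be excluded, and no section requires a symmetric scale. The other annex forms weigh somewhat against a dropped line: the ODI items run unbroken from 0 to 5 points and the satisfaction form shows all five options. That falls short of proof. The wording of the stem does not depend on this question.

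Finally, it is tempting to call the form redundant with SF-12 question 1. That item rates current health from excellent to poor, whereas the PGI-I asks about change since the study began. They overlap only in part.

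**Conclusion.** The inconsistency is real and can be confirmed by reading sections 1, 5.3.5 and 7.6 against the form at 15.2.4. Used as printed, the form yields ratings of global change in health that cannot be reported as improvement in pain. All scheduled PGI-I answers are affected, roughly 396 to 496 depending on losses.

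The point reaches no further than this secondary endpoint. The primary comparison on VAS at 6 months and the 62 per group stand apart from it.

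The conclusion assumes that the annex form is the one patients will complete; no other PGI-I form appears in the documents. The uneven response list is a lesser point and holds only if the form itself shows the same six options. The documents do not show whether version 1.0 is already in use.

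**What to change.** Make the form and the endpoint agree, in one of two ways:

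1. If improvement in pain is intended, reword the stem to ask about change in pain since the study treatment, for example *Since the study treatment, my pain is:*. Anchoring to treatment follows from 5.3.5, which concerns improvement with the procedure, and from the visit plan, in which treatment can come after screening and baseline.
2. If a global rating is intended, keep the form's subject and change sections 1, 5.3.5 and 7.6 to say general health.

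Under either option, check the form for the missing worsening step and add *Much worse* between the two existing options if it is absent. Correct the heading of 15.2.4 and issue a new form version. If any patient has completed version 1.0, report those answers separately, as general health, and do not pool them with answers on pain.

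The cost is one form revision, or an edit to three sections of text. No visits are added and the sample size does not change.

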15.2.5. Subject Satisfaction

SUBJECT SATISFACTION

Sponsor: Fundación Investigación HM Hospitales

Principal Investigator: [name] [name]

Protocol Code: EPIPUL

Form Version: 1.0 of 26th of July 2019

How satisfied are you with the treatment?

Very satisfied

Satisfied

Not sure

Dissatisfied

Very dissatisfied
